10.3.4. Reporting of SAEs

SAE Reporting to Pfizer Safety via an Electronic DCT

- The primary mechanism for reporting an SAE to Pfizer Safety will be the electronic DCT.
- If the electronic system is unavailable, then the site will use the paper SAE DCT (see next section) to report the event within 24 hours.
- The site will enter the SAE data into the electronic DCT (eg, eSAE or PSSA) or paper form (as applicable) as soon as the data become available.
- After the study is completed at a given site, the electronic DCT will be taken off-line to prevent the entry of new data or changes to existing data.
- If a site receives a report of a new SAE from a study participant or receives updated data on a previously reported SAE after the electronic DCT has been taken off-line, then the site can report this information on a paper SAE form (see next section) or to Pfizer Safety by telephone.

SAE Reporting to Pfizer Safety via the CT SAE Report Form

- Facsimile transmission of the CT SAE Report Form is the preferred method to transmit this information to Pfizer Safety.
- In circumstances when the facsimile is not working, an alternative method should be used, eg, secured (Transport Layer Security) or password-protected email. If none of these methods can be used, notification by telephone is acceptable with a copy of the CT SAE Report Form sent by overnight mail or courier service.
- Initial notification via telephone does not replace the need for the investigator to complete and sign the CT SAE Report Form pages within the designated reporting time frames.

10.4. Appendix 4: Contraceptive and Barrier Guidance

10.4.1. Male Participant Reproductive Inclusion Criteria

Male participants are eligible to participate if they agree to the following requirements during the intervention period and for at least 28 days after the last dose of study intervention, which corresponds to the time needed to eliminate reproductive safety risk of the study intervention(s):

- Refrain from donating sperm.

PLUS either:

- Be abstinent from heterosexual intercourse as their preferred and usual lifestyle (abstinent on a long-term and persistent basis) and agree to remain abstinent.

OR

- Must agree to use contraception/barrier as detailed below:
 - Agree to use a male condom, and should also be advised of the benefit for a female partner to use a highly effective method of contraception, as a condom may break or leak, when having sexual intercourse with a WOCBP who is not currently pregnant.

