4.2.2. Choice of Contraception/Barrier Requirements

Nonclinical studies suggest risk for severe manifestations of developmental toxicity at relevant clinical exposures for PF-07284890. Therefore, the use of a highly effective method of contraception is required (see [Appendix 4](#)).

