5.3.1. Contraception

The investigator or their designee, in consultation with the participant, will confirm that the participant is utilizing an appropriate method of contraception for the individual participant and their partner(s) from the permitted list of contraception methods (see [Appendix 4](#), Section 10.4.4) and will confirm that the participant has been instructed in its consistent and correct use. At time points indicated in [SoA](#), the investigator or designee will inform the participant of the need to use highly effective contraception consistently and correctly and document the conversation and the participant's affirmation in the participant's chart. Participants need to affirm their consistent and correct use of at least 1 of the selected methods of contraception, considering that their risk for pregnancy may have changed since the last visit.

In addition, the investigator or designee will instruct the participant to call immediately if the selected contraception method is discontinued and document the requirement to use an alternate protocol-specified method, including if the participant will no longer use abstinence as the selected contraception method, or if pregnancy is known or suspected in the participant or partner.

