10.4.3. Woman of Childbearing Potential

A woman is considered fertile following menarche and until becoming postmenopausal unless permanently sterile (see below).

If fertility is unclear (eg, amenorrhea in adolescents or athletes) and a menstrual cycle cannot be confirmed before the first dose of study intervention, additional evaluation should be considered.

Women in the following categories are not considered WOCBP:

1. Premenopausal female with 1 of the following:
 - Documented hysterectomy;

- Documented bilateral salpingectomy;
- Documented bilateral oophorectomy.

For individuals with permanent infertility due to a medical cause other than the above (eg, mullerian agenesis, androgen insensitivity), investigator discretion should be applied to determining study entry.

Note: Documentation for any of the above categories can come from the site personnel's review of the participant's medical records, medical examination, or medical history interview. The method of documentation should be recorded in the participant's medical record for the study.

2. Postmenopausal female.

- A postmenopausal state is defined as no menses for 12 months without an alternative medical cause. In addition:
 - A high FSH level in the postmenopausal range must be used to confirm a postmenopausal state in women under 60 years old and not using hormonal contraception or HRT.
 - A female on HRT and whose menopausal status is in doubt will be required to use one of the highly effective nonestrogen hormonal contraception methods if she wishes to continue her HRT during the study. Otherwise, she must discontinue HRT to allow confirmation of postmenopausal status before study enrollment.

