10.4.4. Contraception Methods

Contraceptive use by men or women should be consistent with local availability/regulations regarding the use of contraceptive methods for those participating in clinical trials.

The following contraceptive methods are appropriate for this study:

Highly Effective Methods That Have Low User Dependency

1. Implantable progestogen-only hormone contraception associated with inhibition of ovulation.
2. Intrauterine device.
3. Intrauterine hormone-releasing system.
4. Bilateral tubal occlusion.

5. Vasectomized partner.

- Vasectomized partner is a highly effective contraceptive method provided that the partner is the sole sexual partner of the WOCBP and the absence of sperm has been confirmed. If not, an additional highly effective method of contraception should be used. The spermatogenesis cycle is approximately 90 days.

Highly Effective Methods That Are User Dependent

6. Combined (estrogen- and progestogen-containing) hormonal contraception associated with inhibition of ovulation:

- Oral;
- Intravaginal;
- Transdermal.

7. Progestogen-only hormone contraception associated with inhibition of ovulation:

- Oral;
- Injectable.

Sexual Abstinence

8. Sexual abstinence is considered a highly effective method only if defined as refraining from heterosexual intercourse during the entire period of risk associated with the study intervention. The reliability of sexual abstinence needs to be evaluated in relation to the duration of the study and the preferred and usual lifestyle of the participant.

Other Effective Methods

9. Progestogen-only oral hormonal contraception where inhibition of ovulation is not the primary mode of action.

10. Male or female condom, with or without spermicide.

11. Cervical cap, diaphragm, or sponge with spermicide.

12. A combination of male condom with either cervical cap, diaphragm, or sponge with spermicide (double-barrier methods).

CCI

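### Section 10.4.1 most naturally limits the male condom duty to partners who are not pregnant, and no other passage expressly requires a barrier with a pregnant partner

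*Protocol*

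**What the plan says.** Protocol Section 10.4.1 (Male Participant Reproductive Inclusion Criteria) bars sperm donation and then gives men two options: long-term abstinence, or a barrier. The barrier option is one sentence with three parts: the agreement to use a male condom, advice that the female partner should consider highly effective contraception because condoms can fail, and a closing clause, "when having sexual intercourse with a WOCBP who is not currently pregnant". The requirement covers the time on treatment, then continues "for at least 28 days after the last dose of study intervention, which corresponds to the time needed to eliminate reproductive safety risk".

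Other passages bear on the point:

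- **Section 4.2.2** gives the reason for the requirement: "Nonclinical studies suggest risk for severe manifestations of developmental toxicity at relevant clinical exposures for PF-07284890". It then requires highly effective contraception and refers to Appendix 4.
- **Section 10.4.3** defines the partner category: "A woman is considered fertile following menarche and until becoming postmenopausal unless permanently sterile". Pregnancy is not among the listed exceptions.
- **Section 5.3.1** has the participant call the site if the chosen method stops, and has the site "document the requirement to use an alternate protocol-specified method, including if the participant will no longer use abstinence". The same sentence ends with the case where "pregnancy is known or suspected in the participant or partner".
- **Section 10.4.4** opens with "The following contraceptive methods are appropriate for this study", and one of its entries is "Male or female condom, with or without spermicide".
- **Section 8.4.5.1** treats insemination of a female partner by a male participant as a reportable exposure, and collects partner pregnancy details until 50 hours after the last dose.

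**The concern.** The stated hazard is harm to a developing fetus. A condom serves two purposes here: it prevents conception, and it keeps drug in semen away from a fetus that already exists. The pregnancy exclusion makes sense for the first purpose and not for the second. If it governs the condom duty, the partner who already carries a fetus is the one left out, and the protocol gives no reason for that.

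What is at stake is protection of a third party who has not consented, in a study of healthy volunteers who expect no benefit. The PK endpoints, the analysis and the sample size are not affected.

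**Working it through.** **1. Which reading of the sentence?** A duty to use a condom needs a stated occasion, and the closing clause is the only one given. The remark about condom failure is set off by commas, so the clause carries back over it to the condom duty as well as to the advice. That is the most natural reading. The alternative attaches the clause only to the advice on partner contraception. It is grammatically possible, and it would leave the condom duty unconditional.

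**2. Does the definition of WOCBP settle it?** No. Under Section 10.4.3 a pregnant woman remains a WOCBP, since pregnancy is not one of the exceptions. Only the last words of the clause in 10.4.1 take her out.

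**3. Does another passage expressly supply the barrier?**

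| Place | What it does | Express barrier with a pregnant partner? |
|---|---|---|
| Synopsis, Ethical Considerations | General male contraception duty | No |
| Schedule of Activities, footnote j | Discussion of contraception | No |
| 4.2.2 | Highly effective contraception, refers to Appendix 4 | No |
| 5.3.1 | Call to the site; alternate method, which can be read to cover partner pregnancy | No |
| 8.4.5.1 | Reporting of exposure | No |
| 10.4.1, abstinence option | Would cover her, but is only one of two options | No |
| 10.4.4 | List of methods | No |

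**4. How much drug is left when a man leaves the unit?** Inputs are the half-life of 5.7 to 10 h (Section 4.2) and planned discharge on Day 4 of Period 3, 72 h after the last dose (Section 4.1 and the Schedule of Activities). The fraction remaining is 0.5^(t / half-life), assuming first-order decline from the time of dosing.

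| Time after dose | Half-life 5.7 h | Half-life 10 h |
|---|---|---|
| 24 h | 0.5^4.21 = 5.4% | 0.5^2.4 = 19% |
| 48 h | 0.5^8.42 = 0.3% | 0.5^4.8 = 3.6% |
| 72 h | 0.5^12.63 = 0.02% | 0.5^7.2 = 0.7% |

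Five half-lives take 5 × 5.7 = 28.5 h to 5 × 10 = 50 h, and leave 0.5^5 = 3.1%. The upper value equals the 50-hour window in Section 8.4.5.1. A completer is past that window at discharge, in line with the statement in Section 5.3.5 that discharge falls more than five half-lives after the last dose. Slower absorption with food would raise these percentages somewhat.

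**5. Who could be affected?** Mainly a man who leaves within about 28.5 to 50 h of one of the three doses and has a pregnant partner. Section 7.2 allows withdrawal at any time. Section 7.1 ends participation after permanent discontinuation for an adverse event or a positive COVID-19 test. The study has about 12 participants in total, and the documents do not say how many men will have a pregnant partner.

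**The case against.** The strongest case against is that this is a possible ambiguity with almost no consequence. The gap depends on one parse of a sentence. Section 5.3.1 already has the investigator confirm a method suited to the individual participant and partner, and has the participant call at once if partner pregnancy is known or suspected. Participants are confined throughout, and Section 7.2 adds an early discontinuation visit where possible. Harm would need an early exit, a pregnant partner, unprotected intercourse within a short window and some transfer through semen. All of this stands, and it limits the point to a minor one. It does not remove it, because an eligibility criterion should not depend on the reader choosing the less natural parse, and a telephone call is not a barrier.

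A reader might infer more than the documents support:

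- **That the protocol deliberately permits unprotected intercourse with a pregnant partner.** The other parse is open, and 5.3.1 can be read to trigger an alternate method in that case.
- **That 5.3.1 would accept a non-barrier method from the 10.4.4 list.** That list serves men and women alike. Section 10.4.1 limits men to abstinence or a condom, and most of the other methods have no purpose once the partner is pregnant.
- **That a fetus would be exposed to a harmful amount.** Percent of drug left in the body is not an amount in semen. The documents give no semen data, and the Investigator's Brochure was not available.
- **That about 25 days of real risk follow discharge** (28 days less 3). This follows from the protocol's own 28-day statement, but the elimination figures above do not show material exposure over that time.

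**Conclusion.** The point holds as a low-cost wording improvement. On its most natural reading, Section 10.4.1 leaves out the pregnant partner, no other passage expressly brings her back in, and the omission does not fit the developmental-toxicity rationale in Section 4.2.2 or the 28-day window that 10.4.1 sets for itself.

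The practical size is small: at most about 0.7% of the drug remains at planned discharge, and more than about 3% only after an exit within roughly 28.5 to 50 h of a dose. These figures assume first-order decline from dosing at half-lives taken from small groups of fasted patients. Seminal transfer, and so fetal exposure, cannot be stated from the documents. Confidence is medium, because the alternative parse cannot be excluded.

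**What to change.** Split the sentence in Section 10.4.1 into two:

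1. The participant agrees to use a male condom, or to be abstinent, for intercourse with any WOCBP, including a pregnant partner, during the intervention period and for at least 28 days after the last dose.
2. Where the partner is a WOCBP who is not pregnant, he is also advised of the benefit of her using highly effective contraception.

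Optionally, state in Section 5.3.1 that when partner pregnancy is known or suspected, the alternate method is a condom or abstinence. If the exclusion is deliberate, one sentence giving the reason would also resolve the point.

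The cost is one sentence, or two with the option, and no added procedures, data or participants. The downside is a slightly broader, time-limited restriction on men with a pregnant partner. The 28-day window is longer than the elimination figures require, but it is the window already applied with other partners.

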10.4.2. Female Participant Reproductive Inclusion Criteria

The criteria below are part of Inclusion Criterion 2 (Section 5.1) and specify the reproductive requirements for including female participants. Refer to [Section 10.4.4](#) for a complete list of contraceptive methods permitted in the study.

A female participant is eligible to participate if she is not a WOCBP (see definition in Section 10.4.3) and is not breastfeeding.

10.4.3. Woman of Childbearing Potential

A woman is considered fertile following menarche and until becoming postmenopausal unless permanently sterile (see below).

If fertility is unclear (eg, amenorrhea in adolescents or athletes) and a menstrual cycle cannot be confirmed before the first dose of study intervention, additional evaluation should be considered.

Women in the following categories are not considered WOCBP:

1. Premenopausal female with 1 of the following:
 - Documented hysterectomy;

- Documented bilateral salpingectomy;
- Documented bilateral oophorectomy.

For individuals with permanent infertility due to a medical cause other than the above (eg, mullerian agenesis, androgen insensitivity), investigator discretion should be applied to determining study entry.

Note: Documentation for any of the above categories can come from the site personnel's review of the participant's medical records, medical examination, or medical history interview. The method of documentation should be recorded in the participant's medical record for the study.

2. Postmenopausal female.

- A postmenopausal state is defined as no menses for 12 months without an alternative medical cause. In addition:
 - A high FSH level in the postmenopausal range must be used to confirm a postmenopausal state in women under 60 years old and not using hormonal contraception or HRT.
 - A female on HRT and whose menopausal status is in doubt will be required to use one of the highly effective nonestrogen hormonal contraception methods if she wishes to continue her HRT during the study. Otherwise, she must discontinue HRT to allow confirmation of postmenopausal status before study enrollment.

10.4.4. Contraception Methods

Contraceptive use by men or women should be consistent with local availability/regulations regarding the use of contraceptive methods for those participating in clinical trials.

The following contraceptive methods are appropriate for this study:

Highly Effective Methods That Have Low User Dependency

1. Implantable progestogen-only hormone contraception associated with inhibition of ovulation.
2. Intrauterine device.
3. Intrauterine hormone-releasing system.
4. Bilateral tubal occlusion.

5. Vasectomized partner.

- Vasectomized partner is a highly effective contraceptive method provided that the partner is the sole sexual partner of the WOCBP and the absence of sperm has been confirmed. If not, an additional highly effective method of contraception should be used. The spermatogenesis cycle is approximately 90 days.

Highly Effective Methods That Are User Dependent

6. Combined (estrogen- and progestogen-containing) hormonal contraception associated with inhibition of ovulation:

- Oral;
- Intravaginal;
- Transdermal.

7. Progestogen-only hormone contraception associated with inhibition of ovulation:

- Oral;
- Injectable.

Sexual Abstinence

8. Sexual abstinence is considered a highly effective method only if defined as refraining from heterosexual intercourse during the entire period of risk associated with the study intervention. The reliability of sexual abstinence needs to be evaluated in relation to the duration of the study and the preferred and usual lifestyle of the participant.

Other Effective Methods

9. Progestogen-only oral hormonal contraception where inhibition of ovulation is not the primary mode of action.

10. Male or female condom, with or without spermicide.

11. Cervical cap, diaphragm, or sponge with spermicide.

12. A combination of male condom with either cervical cap, diaphragm, or sponge with spermicide (double-barrier methods).

CCI

10.6. Appendix 6: Liver Safety: Suggested Actions and Follow-Up Assessments

Potential Cases of Drug Induced- Liver Injury

Humans exposed to a drug who show no sign of liver injury (as determined by elevations in transaminases) are termed “tolerators,” while those who show transient liver injury but adapt are termed “adaptors.” In some participants, transaminase elevations are a harbinger of a more serious potential outcome. These participants fail to adapt and therefore are “susceptible” to progressive and serious liver injury, commonly referred to as DILI. Participants who experience a transaminase elevation above $3 \times$ ULN should be monitored more frequently to determine if they are “adaptors” or are “susceptible.”

In the majority of DILI cases, elevations in AST and/or ALT precede T bili elevations ($>2 \times$ ULN) by several days or weeks. The increase in T bili typically occurs while AST/ALT is/are still elevated above $3 \times$ ULN (ie, AST/ALT and T bili values will be elevated within the same laboratory sample). In rare instances, by the time T bili elevations are detected, AST/ALT values might have decreased. This occurrence is still regarded as a potential DILI. Therefore, abnormal elevations in either AST OR ALT in addition to T bili that meet the criteria outlined below are considered potential DILI (assessed per Hy’s law criteria) cases and should always be considered important medical events, even before all other possible causes of liver injury have been excluded.

The threshold of laboratory abnormalities for a potential DILI case depends on the participant’s individual baseline values and underlying conditions. Participants who present with the following laboratory abnormalities should be evaluated further as potential DILI (Hy’s law) cases to definitively determine the etiology of the abnormal laboratory values:

- Participants with AST/ALT and T bili baseline values within the normal range who subsequently present with AST OR ALT values $\geq 3 \times$ ULN AND a T bili value $\geq 2 \times$ ULN with no evidence of hemolysis and an alkaline phosphatase value $< 2 \times$ ULN or not available.
- For participants with baseline AST **OR** ALT **OR** T bili values above the ULN, the following threshold values are used in the definition mentioned above, as needed, depending on which values are above the ULN at baseline:
 - Preexisting AST or ALT baseline values above the normal range: AST or ALT values ≥ 2 times the baseline values AND $\geq 3 \times$ ULN; or $\geq 8 \times$ ULN (whichever is smaller).
 - Preexisting values of T bili above the normal range: T bili level increased from baseline value by an amount of $\geq 1 \times$ ULN **or** if the value reaches $\geq 3 \times$ ULN (whichever is smaller).

Rises in AST/ALT and T bili separated by more than a few weeks should be assessed individually based on clinical judgment; any case where uncertainty remains as to whether it represents a potential Hy’s law case should be reviewed with the sponsor.

The participant should return to the investigator site and be evaluated as soon as possible, preferably within 48 hours from awareness of the abnormal results. This evaluation should include laboratory tests, detailed history, and physical assessment.

In addition to repeating measurements of AST and ALT and T bili for suspected Hy's law cases, additional laboratory tests should include albumin, CK, direct and indirect bilirubin, GGT, PT/INR, total bile acids, and alkaline phosphatase. Consideration should also be given to drawing a separate tube of clotted blood and an anticoagulated tube of blood for further testing, as needed, for further contemporaneous analyses at the time of the recognized initial abnormalities to determine etiology. A detailed history, including relevant information, such as review of ethanol, acetaminophen/paracetamol (either by itself or as a coformulated product in prescription or over-the-counter medications), recreational drug, or supplement (herbal) use and consumption, family history, sexual history, travel history, history of contact with a jaundiced person, surgery, blood transfusion, history of liver or allergic disease, and potential occupational exposure to chemicals, should be collected. Further testing for acute hepatitis A, B, C, D, and E infection, liver imaging (eg, biliary tract), and collection of serum samples for acetaminophen/paracetamol drug and/or protein adduct levels may be warranted.

All cases demonstrated on repeat testing as meeting the laboratory criteria of AST/ALT and T bili elevation defined above should be considered potential DILI (Hy's law) cases if no other reason for the LFT abnormalities has yet been found. **Such potential DILI (Hy's law) cases are to be reported as SAEs, irrespective of availability of all the results of the investigations performed to determine etiology of the LFT abnormalities.**

A potential DILI (Hy's law) case becomes a confirmed case only after all results of reasonable investigations have been received and have excluded an alternative etiology.

